5.2.2 Time-to-Event

Both, formal and informal summary analyses on time-to-event endpoints will be performed. That is to say, Kaplan-Meier analyses will be performed, and summary statistics will be calculated.

Progressive disease: Progressive disease (PD or NEVCPD) is level=5 as outlined in the endpoint 'Unconfirmed Overall Response' in [Section 5.2.1](#) above.

Date of progressive disease is the earliest of:

- 1) date of progression (progdt) recorded on course in e-CRF corresponding to first recurrence of progressive disease

- 2) date of progression recorded (progdt) on end of trial in e-CRF if first recurrence of progressive disease was at end of trial
- 3) date of progressive disease recorded on post-study follow-up of eCRF
- 4) death date (in the case of none of 1-3 being available)

Patients administered a new additional other anti-cancer therapy recorded in the e-CRF but not presenting with progressive disease before the start of this new anti-cancer therapy will be censored at the date of last radiological imaging before the new anti-cancer therapy has started.

Patients not administered another anti-cancer therapy and not presenting with progressive disease or death during the trial will be censored at the date of the last imaging during which the patient was evaluable and did not have the event. Alternatively, if there is an investigators assessment after this, then the date of the NEVCNPD will be used.

Progression-free survival (PFS) [in days] is therefore the time from first administration of trial medication to the earlier of progressive disease or death. (Date of PD as above – date of first administration of trial medication + 1).

Progression-free survival (PFS) censored [in days] is therefore the time from first administration of trial medication to the date of last imaging (or NEVCNPD as above). (Date of last imaging – date of first administration of trial medication + 1, or Date of NEVCNPD – date of first administration of trial medication + 1).

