7. PLANNED ANALYSIS

For the production of summary tables, standard programs [REDACTED] will be used if available.

The following standard descriptive statistical parameters will be the basis for displays in summary tables of continuous variables. [REDACTED]

N	Number of non-missing values
Min	Minimum value
Q1	Lower quartile (25% percentile)
Median	Median value
Q3	Upper quartile (75% percentile)
Max	Maximum value

The following standard descriptive statistical parameters will be displayed in frequency tables of categorical or categorised variables:

N	number of non-missing observations
%	percentage

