7.5 SECONDARY ENDPOINTS

The following endpoints relating to tumour response will be summarised descriptively in tables, by initial treatment:

- Unconfirmed Overall Response at all timepoints
- Unconfirmed Best Overall Response

- Unconfirmed Best Objective Response
- Clinical Benefit
- Confirmed Best Objective Response

Progression Free Survival: If applicable, for PFS a Kaplan-Meier analyses will be performed on the MTD dose group and other cohorts of interest, depending on the final DLT results. Additionally, this information will be listed, including whether or not the endpoint has been censored.

For the ECOG score, the following endpoints will be summarised in tables:

- ECOG score changes at the end of treatment
- Scale of ECOG score changes at the end of treatment.

The analysis of PK parameters is performed [REDACTED] and will be reported separately by the PK department within BI.

The calculation of the pharmacokinetic parameters as well as the descriptive analysis of the concentration values and the descriptive and comparative analysis of the pharmacokinetic parameters is based on the [REDACTED] reference document.

Tables and figures for concentrations values and PK parameters will be created according to the reference document 'Graphs and Tables for Clinical Pharmacokinetic Noncompartmental Analyses'.

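### SAP 5.2.2 plans informal summary statistics for PFS without saying how censored times enter, and its visible censoring formula has no floor for patients with only a baseline scan

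*SAP*

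**What the plan says.** SAP 5.2.2 begins "Both, formal and informal summary analyses on time-to-event endpoints will be performed" and explains this as follows: "That is to say, Kaplan-Meier analyses will be performed, and summary statistics will be calculated". It names no statistics and gives no treatment of censored times. SAP section 7 sets the default: "The following standard descriptive statistical parameters will be the basis for displays in summary tables of continuous variables". The list that follows is N, minimum, quartiles, median and maximum.

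For PFS output, SAP 7.5 says "If applicable, for PFS a Kaplan-Meier analyses will be performed on the MTD dose group and other cohorts of interest" and "Additionally, this information will be listed, including whether or not the endpoint has been censored". It names no descriptive PFS table.

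On censoring, SAP 5.2.2 has two rules:

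- A patient with no new anti-cancer therapy, progression or death "will be censored at the date of the last imaging during which the patient was evaluable and did not have the event", or at a later investigator assessment of non-evaluable but clinically not progressive disease (NEVCNPD).
- A patient who starts new therapy before progressing is censored at the last imaging before that therapy. No NEVCNPD alternative is given.

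The censored time is "Date of last imaging – date of first administration of trial medication + 1".

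Protocol 7.4 differs. An early stop unrelated to the disease is censored at end of treatment (EOT), and patients with no tumour assessment in the six weeks before discontinuation are reviewed case by case.

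**The concern.** There are two separate issues.

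First, an ordinary median or quartile is not a valid summary of a censored time. If censored times are pooled with event times, each counts as if progression had occurred on that day. If they are left out, the patients who lasted longest tend to be removed. Either way the summary tends to be short, by an amount that depends on how many patients were censored. PFS carries the protocol's secondary question on time to progression, so a reader would take such a number as an efficacy result.

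Second, the last evaluable imaging can be the baseline scan, which normally precedes dosing. The formula then returns zero or a negative number of days, and no visible text prevents it.

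**Working it through.** The plan gives no PFS median, censoring share or event count, so there is no figure of its own to reproduce. Every PFS size below rests on stated assumptions.

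**1. Plain median under censoring.** Let PFS be exponential with rate L and censoring exponential with rate M. The censored share is c = M/(L+M).

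- Over all times, min(T, C) is exponential with rate L+M, so its median is ln2/(L+M) = (1-c) × ln2/L.
- Over events only, T given T < C is also exponential with rate L+M, so the result is the same.

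For an assumed true median of 60 days:

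- c = 20%: 0.8 × 60 = 48
- c = 30%: 0.7 × 60 = 42
- c = 40%: 0.6 × 60 = 36

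With Weibull shape 1.5 and 30% censored, simulation gives 44.5 days (all times) and 49.9 (events only). The direction holds, but the exact factor depends on the model.

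**2. The same question with a scan schedule.** The simulation took 24 patients (the planned number at MTD, Protocol 3.1), scans every 42 days (imaging at the end of every other 21-day course) and exponential progression detected at the next scan. A stated share of patients was assigned a possible censoring scan; it counted only if it came before progression. Mean medians over 1,500 repeats, in days:

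| True median | Assigned censoring | Plain, all times | Plain, events only | Kaplan-Meier |
|---|---|---|---|---|
| 90 | 0% | 115.1 | 115.1 | 109.4 |
| 90 | 20% | 100.4 | 104.1 | 111.2 |
| 90 | 40% | 92.0 | 95.0 | 113.9 |
| 150 | 0% | 175.3 | 175.3 | 166.5 |
| 150 | 40% | 119.3 | 141.1 | 179.8 |

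Detection at the next scan lifts all values above the true median. The plain median falls as censoring rises. Kaplan-Meier does not fall; it drifts up slightly. The gap in the 0% rows comes from how an even-sized sample's median is taken.

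**3. The censoring formula.** A last scan d days before dosing gives a time of -d + 1:

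- d = 0 gives 1
- d = 1 gives 0
- d = 2 gives -1
- d = 14 gives -13
- d = 28 gives -27

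SAP Table 6.2: 1 lists a baseline scan more than four weeks before treatment as a violation, so the range within the plan is -27 to +1. The first scheduled post-dose scan falls at about day 2 × 21 + 1 = 43.

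**4. Does the negative sign matter?** Take 12 constructed patients: five events at day 43; two events and one censored at 85; one event and one censored at 127; one censored at each of 169 and 211. Kaplan-Meier is 7/12 = 0.583 after day 43 and 0.583 × 5/7 = 0.417 after day 85, so the median is 85.

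Add two patients with only a baseline scan, at -27 and -13. Both leave before the first event, so 12 are still at risk at day 43 and the Kaplan-Meier median stays 85. The plain all-times median becomes (43+85)/2 = 64. With both set to day 1 the plain median is still 64, the first quartile is still 43, and only the minimum changes, from -27 to 1.

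The simulation agrees. With a true median of 90, 20% assigned censoring and 10% baseline-only patients, the plain median is 89.8 either way and Kaplan-Meier is 114.2 either way. The mean moves from 123.1 to 124.5, but the mean is not in the SAP's default list.

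**The case against.** The best defence is that the invalid summary is inferred. SAP 5.2.2 does not define its summary statistics; they could be Kaplan-Meier quartiles with counts. SAP 7.5 lists the response endpoints to be tabulated, and PFS is not among them. A reader might conclude that a table of PFS biased low is planned, or that cohorts without Kaplan-Meier will have a plain median as their only result. The documents do not establish either: the output named for every cohort is a listing. What stands is that 5.2.2 sets informal statistics against the formal Kaplan-Meier analysis, and the only summary set visible in the SAP is the default quantiles. The natural reading is therefore a summary that ignores censoring, and 5.2.2 and 7.5 do not match.

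On the formula, a reader might infer that every patient with no scan after dosing gets a negative time. That is too wide. Progression, clinical progression without evaluable lesions (NEVCPD) and death are events with positive times. A later NEVCNPD date rescues patients without new therapy. Protocol 6.2.3 also indicates end-of-trial imaging unless it was done in the past three weeks. This narrows the gap without closing it: a scan 5 days before dosing and a last visit on day 15 are 5 + 14 = 19 days apart, so no repeat would be needed, and Appendix 10.4.4 makes measurements after discontinuation optional. Parts of SAP 6.6 are redacted just after the progression-date rule, so a floor may exist there.

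PFS is secondary, everything is descriptive, and SAP 3.2 disclaims comparison of cohorts. That limits the weight of the point. It does not make an ordinary median of censored times a sound description.

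**Conclusion.** The point holds as an ambiguity with a likely invalid reading, plus a small gap in a formula. If the informal statistics are ordinary quantiles, they understate PFS by an amount that grows with censoring: 20% to 40% of the median at 20% to 40% censored under the exponential model, less in the Weibull case. These sizes depend wholly on assumed medians and censoring shares.

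The two issues should not be joined as cause and effect. It is tempting to say that negative times make PFS biased low, but they move neither the Kaplan-Meier curve nor, compared with day 1, the plain median. The shortfall comes from ignoring censoring and from counting baseline-only patients as very short times. The formula's harm is confined to impossible values in the listing and the minimum. It affects mainly patients who start new anti-cancer therapy before the first post-dose scan.

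The visible SAP also departs from the protocol's EOT censoring rule, and SAP section 4 does not mention it. The protocol text available is dated 3 October 2005, and the SAP cites three later amendments, so one of them may explain the change.

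**What to change.** In SAP 5.2.2, replace the informal summary statistics with Kaplan-Meier quartiles and confidence limits, and the numbers of events and censored patients, wherever Kaplan-Meier is applied. Rely on the listing already planned in 7.5 for small cohorts, and make the two sections agree.

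Add one sentence: a treated patient with no post-dose assessment and no event is censored at day 1. State how this fits with Protocol 7.4, which would place some of the same patients at EOT, and record the chosen rule in SAP section 4 if it departs from the protocol.

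The cost is a few sentences of SAP text. Some cohorts will show a quartile or median as not estimable, which is the honest result for three to six patients with censoring. Pooling lower dose tiers is optional and not part of this change.

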5.2.3 Eastern Cooperative Oncology Group (ECOG) Performance Score

ECOG score: The scale of ECOG score is defined as a six point categorical scale as described in ([R01-0787](#)) ranging from 0 (asymptomatic) to 5 (death). Calculation was to be carried out for each patient, for each first visit of each treatment course, each last visit of each treatment course, the end of treatment and the follow up visit.

ECOG score change from baseline to end of treatment will be calculated, and defined as

= ECOG score at end of treatment – ECOG score at baseline.

Scale of ECOG score change: The ECOG score changes from baseline score will be categorized on a three point categorical scale: deteriorated, unchanged, and improved. Improvement or deterioration of performance status will require a decrease or an increase from baseline, respectively, of at least one point on the ECOG scale.

5.2.4 Adverse events

Adverse events (AEs) are defined as the same preferred term (PT) after collapsing of two events less than 24 hours apart.

Intensity of adverse events is scaled according to Common Terminology Criteria of Adverse Event (CTCAE version 3.0, [R06-1666](#)).

A separate listing for all patients who developed the following events will be generated.

- AEs with CTCAE grade ≥ 3 ,
- DLT,
- serious AEs, or,
- significant AEs as defined in Section [7.7.1.2](#)

5.2.5 Laboratory parameters

In this trial the original laboratory values will be converted into standard units and CTCAE grades for parameters which have a CTCAE criteria (For definition of CTCAE grade for laboratory values, [REDACTED]). For this study, the laboratory parameters and their functional groups [REDACTED]

[REDACTED] together with the direction of concern, which were to be recorded and which have a CTCAE criteria are:-

Haematology: Haemoglobin (-), white blood cell (WBC) (-) and Platelets (-)

Differentials: Neutrophils (-) and Lymphocytes (-)

Coagulation: International normalized ratio of prothrombin time (INR) (+) and Partial thromboplastin time (PTT) (+)

Electrolytes: Sodium (+ and -), Potassium (+ and -) and Calcium (+ and -)

Enzymes: Aspartate aminotransferase (AST) (+), Alanine aminotransferase (ALT) (+) and Alkaline phosphatase (ALKP) (+)

Substrates: Total bilirubin (+), Glucose (+ and -), Creatinine (+), Albumin (-) and Creatinine Phosphokinase (CPK) (+)

+ (-) means the higher (lower) the value the worse the toxicity. (+ and -) means the parameter can be considered as hyper or hypo.

It is important to note that these are only the parameters that have a CTCAE criteria, and that other parameters were recorded which have no CTCAE criteria.

Laboratory parameters were to be recorded for each patient on days 0-3, 5, 8, 15 and 22 of first treatment course, and all except days 3 and 5 at subsequent treatment courses. Recording of standard laboratory parameters was optional at follow-up. Changes from baseline will be calculated for each day of the first treatment course where measured, the last visit of each treatment course and the end of the trial. For the CTCAE grades, some changes from other time-points will also be calculated.

The baseline, last value on treatment and corresponding change from baseline will be presented using N, median and interquartile range. This will be done for all continuous laboratory parameters using the Boehringer Ingelheim (BI) normalised values, except, however, in the case of WBC differentials (Neutrophils and Lymphocytes) which have been

recorded in percentage. These have been re-derived to normalised values in such a way that the accuracy of decimal places is maintained for longer. [REDACTED]

Patients with clinically relevant laboratory abnormalities, [REDACTED] will be summarised.

Note: For calculating the change in CTCAE grade from baseline/ pre-dose level, patients with a CTCAE grade of -9 will be reviewed on a case-by-case basis. If there is no suggestion that the corresponding laboratory value is of clinical significance, these values will be changed to -7 and treated as a CTCAE grade of 0 for analyses. All other values with CTCAE grade -9 will be regarded as CTCAE grade -8. Values with a CTCAE grade of -8 will either be removed from analyses concerning determination of baseline and worst CTCAE grade or if needed the category “not covered by CTC criteria” will be included. Values with CTCAE grades of -7 and -8 will be displayed in two separate listings.

In a similar manner, patients with a CTCAE grade of -1 will be reviewed on a case-by-case basis. For uric acid, values with CTCAE grade -1 will be regarded as either CTCAE grade 3 or CTCAE grade 1, depending on whether accompanied with physiological consequences or not.

The worst post baseline laboratory value and its CTCAE grade over all treatment courses will be calculated for each laboratory parameter specified above.

The time to worst CTCAE value [in days] will be defined as the time from first administration of trial medication to the first occurrence of the worst CTCAE grade. (Date of first occurrence of worst CTCAE grade – date of first administration of trial medication + 1).

The last value on treatment will be determined using a similar algorithm to the adverse events, and presented descriptively.

The change of the CTCAE grade of the lab value will be calculated

- from baseline to the last laboratory value on treatment
- from baseline to the worst value on treatment

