### 7.3.3 Safety analyses

Key measures of safety will include:

- the incidence and intensity (according to CTCAE criteria version 3.0) of adverse events
- time course and distribution of patients by maximum CTCAE grade; and
- time course of laboratory changes

The type, number and intensity of adverse events will indicate how well BI 6727 is tolerated. Haematological toxicity such as thrombocytopenia, neutropenia and leukopenia as well as non-haematological toxicity will be evaluated continuously by using the CTCAE scheme.

Specific AE expected to be associated with BI 6727 may be described more accurately.

Frequency distributions and other descriptive statistical measures will be used to examine these variables. The time course of the changes and the reversibility will be displayed.

Descriptive statistics for ECG, in addition to abnormalities and other notable findings will also be analysed.

All data will be presented in the following segments:

- 1. First course of BI 6727
- 2. Data collected overall courses of BI 6727

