6.3 PATIENT SETS ANALYSED

Only one analysis population (Treated Set) will be considered for efficacy and safety (except ECG).

The Treated Set consists of all patients who received at least one application of the BI drug BI 6727.

Trial medication is defined as BI 6727.

First administration of trial medication is defined as date of first administration of BI 6727.

ECG

Per protocol set (PPS):

This is a subset of the Treated Set, restricted to patients, who have an ECG assessment in both courses (e.g. patients, who were replaced will be excluded).

[REDACTED]

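### Time to worst laboratory CTCAE grade (SAP 5.2.5) has no worsening condition and runs from the first dose of the trial, so a summary of it would not show when toxicity follows an infusion (minor)

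*SAP*

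**What the plan says.** SAP 5.2.5 builds the variable in two steps. First: "The worst post baseline laboratory value and its CTCAE grade over all treatment courses will be calculated for each laboratory parameter specified above". Second, the time to that grade, in days, "will be defined as the time from first administration of trial medication to the first occurrence of the worst CTCAE grade". The formula beside it takes the "Date of first occurrence of worst CTCAE grade", subtracts the date of first administration and adds one day. SAP 6.3 fixes the starting point as a single date per patient: "First administration of trial medication is defined as date of first administration of BI 6727".

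SAP 5.2.5 keeps grade 0 as an analysed category. Certain values without a regular grade, if judged not clinically significant, are "treated as a CTCAE grade of 0 for analyses". Values coded -8 may be removed when baseline and worst grade are determined.

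On sampling, SAP 5.2.5 states: "Laboratory parameters were to be recorded for each patient on days 0-3, 5, 8, 15 and 22 of first treatment course". In later courses days 3 and 5 are dropped. The visit list in Protocol 6.2.2.1 places the day 1 sample before the infusion, so the first post-dose sample is on day 2.

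On timing in general, Protocol 7.3.3 says of the safety variables: "The time course of the changes and the reversibility will be displayed". Protocol 7.1.1 and 7.3.3 ask for the first course and all courses to be presented separately.

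**The concern.** The definition has two features that make the number hard to read.

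- **No worsening condition.** A patient who stays at grade 0, or at the baseline grade, still has a worst post-baseline grade. Its first occurrence is normally the first post-dose sample, so the value comes from the visit schedule and not from toxicity.
- **One clock for all courses.** BI 6727 is given on day 1 of every three-week course. If the worst grade first appears in a later course, the value includes all the time spent in earlier courses.

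The protocol (1.2 and 1.4) reports neutropenia as dose limiting with the related inhibitor BI 2536 and expects bone marrow effects with BI 6727. For such an effect the useful quantity is the day after an infusion on which the worst grade is seen. A median of this variable would mix schedule-driven values near day 2 with values that grow by about three weeks per course. It could be taken for a nadir day, which it is not.

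**Working it through.** The plan states no figure for this variable, so there is nothing to reproduce. The check applies the SAP formula to the SAP schedule.

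**Inputs**
- Starting point: date of first BI 6727 administration, one per patient (SAP 5.2.5, 6.3).
- Scope of worst: all courses, post-baseline (SAP 5.2.5).
- Interval between infusions: 21 days (Protocol synopsis; SAP 3.2). Visit windows shift the results by a few days.
- Post-dose laboratory days: 2, 3, 5, 8, 15 and 22 in course 1; 2, 8, 15 and 22 later (SAP 5.2.5).

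**Formula.** T = date of first occurrence of worst grade − date of first dose + 1. For day d of course c without delays, T = 21 × (c − 1) + d.

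**Patient without worsening.** Grade 0 at baseline and at every later sample: the worst grade is 0, first seen on day 2, so T = 2. A patient who stays at grade 1 throughout also gets T = 2. There are exceptions. With baseline grade 1, day 2 grade 0 and day 8 grade 1, T = 8, again without worsening. A patient whose only values are coded -8 may have no value at all.

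**Same event, different course.** Worst grade on day 15 of its course:

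| Course | 1 | 2 | 3 | 4 | 5 | 6 |
|---|---|---|---|---|---|---|
| T (days) | 15 | 36 | 57 | 78 | 99 | 120 |

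For course 3: 21 × 2 + 15 = 57. Protocol 3.3.3 allows up to 6 weeks from the start of the previous course. With two such intervals the same event gives 2 × 42 + 15 = 99.

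**Effect on a cohort of three.** Two patients never worsen (T = 2 each) and one reaches grade 4 on day 15 of course 1 (T = 15). The median of (2, 2, 15) is 2. Restricted to patients who worsen, the result is N = 1, course 1, day 15, with two patients not worsening.

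**Illustrative simulation.** The inputs are assumptions, not taken from the documents: the worst value of a course falls on day 8 (30%) or day 15 (70%); grades 1 to 4 are drawn independently per course with probabilities 0.25, 0.35, 0.25 and 0.15; patients who do not worsen are scored on day 2; 200,000 patients per scenario. Entries are median (quartiles) in days.

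| Share who worsen, courses | As written | Worsened only, first-dose clock | Worsened only, day within course |
|---|---|---|---|
| 30%, 4 courses | 2 (2–15) | 36 (15–57) | 15 (8–15) |
| 70%, 4 courses | 15 (2–36) | 36 (15–57) | 15 (8–15) |
| 90%, 6 courses | 36 (15–78) | 36 (15–78) | 15 (8–15) |

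The timing within a course is the same in every row. As written, the median depends on the share of patients who worsen and on the number of courses. Removing patients without worsening does not by itself recover the day after infusion, so the two features act separately.

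**The case against.** Several counter-arguments carry weight.

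- **No summary of the variable is visibly planned.** SAP 7.7.2 lists maximum grades, shift and transition tables, time-course graphs and relevant abnormalities, but not time to worst grade. It might only be listed, or it might be summarised under the general rules of SAP 7. A misleading median is therefore possible, not announced. This stands.
- **Timing is partly covered elsewhere.** A reader might infer that the plan leaves the timing of neutropenia undescribed. The documents do not support that. SAP 7.7.2 plots neutrophils, white cells and platelets over time and tabulates maximum grades by course. SAP 5.2.5 calculates changes from baseline for each measured day of course 1. Table 6.1.3: 1 provides a course 1 analysis for laboratory values. The display promised in Protocol 7.3.3 is met by the graphs. None of this alters the variable itself, which is still defined over all courses.
- **The first-dose clock has a use.** It shows whether the worst grade comes early or late in treatment, and the protocol raises accumulation over courses itself (1.4). The SAP uses the same starting point for PFS and exposure. It would go too far to call this clock wrong, and it should be kept.
- **Inclusion of patients without worsening is inferred from silence.** A restriction could stand in redacted text or in the laboratory guideline that SAP 7.7.2 cites. That is possible, but the visible rule contains none.
- **Sampling is sparse.** With planned days 2, 3, 5, 8, 15 and 22, even a better variable locates a nadir only roughly. This is true, but it does not justify adding schedule-driven values.

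**Conclusion.** The point holds as a minor one. The visible definition usually gives a schedule-driven value, typically day 2, to patients whose grade never exceeds baseline. It also adds the elapsed time of earlier courses to worst grades that first appear later: day 57 instead of course day 15 in course 3 without delays. For a patient who worsens and whose worst grade falls in course 1, the value is correct. The distortion arises when these kinds of value are summarised together.

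Two stronger readings are not supported. A reader might infer that every patient gets a value and that it is always day 2 when nothing worsens; removal of -8 values and fluctuating grades are exceptions. A reader might also infer that the MTD or the phase II dose is at risk. It is not: DLT is determined separately, the analyses are descriptive (SAP 3.3), and this is one secondary laboratory variable.

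The conclusion assumes that no worsening condition exists in redacted or external text and that infusions are 21 days apart. The simulation only illustrates the direction and possible size of the effect.

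**What to change.** In SAP 5.2.5:

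1. Compute the variable, for each parameter, only in patients whose worst post-baseline grade exceeds the baseline grade. Report the number without worsening beside it.
2. Keep the time from first dose. Add the course in which the worst grade first occurs and the day within that course, counted from that course's infusion.
3. Show course 1 separately from the result over all courses.
4. State whether the variable is tabulated or only listed. If a worsening condition already exists in another specification, repeat it here.

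The cost is a few lines of SAP text and one or two derived variables from dates already collected; no new data are needed. The drawback is a smaller N in low-dose cohorts, where few patients may worsen and individual values may say more than a median.
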